17.1.4. PRIMARY ANALYSIS OF PRIMARY EFFICACY VARIABLE(S)

The following hypotheses (H01 and H02) for the primary endpoint will be tested:

H₀₁: The percentage change from Baseline in esophageal PEC at Week 16 is the same between etrasimod 2mg and placebo.

H₁₁: The percentage change from Baseline in esophageal PEC at Week 16 is different between etrasimod 2mg and placebo.

H₀₂: The percentage change from Baseline in esophageal PEC at Week 16 is the same between etrasimod 1mg and placebo.

H₁₂: The percentage change from Baseline in esophageal PEC at Week 16 is different between etrasimod 1mg and placebo.

All hypotheses will be tested at the 2 sided α level, 0.05.

The primary efficacy analysis will be performed for the FAS. Percent change from baseline in esophageal PEC will be summarized using the number of observations, mean, standard deviation (SD), median, minimum, and maximum. An analysis of covariance (ANCOVA) model based on rank scores due to the skewed distribution of the data and possible outliers will be used. The ANCOVA model will include treatment group and randomization stratification factors of Baseline history of esophageal dilation (Yes/No) and concurrent PPI therapy (Yes/No) as factors and Baseline eosinophil PEC as a covariate. Multiple results of the ANCOVA model will be expressed as least square (LS) means rank scores, LS mean rank scores difference from placebo, 95% confidence interval (CI) and p-value. For the treatment comparisons of etrasimod 1 mg vs. placebo and etrasimod 2 mg vs placebo, the treatment group factor in the ANCOVA model will include placebo, etrasimod 1 mg and etrasimod 2 mg. For the comparison of etrasimod any dose vs placebo, a separate ANCOVA model based on rank scores will be used, where treatment group factor will only include placebo and etrasimod any dose treatment. For the Extension Treatment Period, no pair-wise comparison will be performed; only descriptive statistics will be provided. In addition, descriptive summary of percentage change in esophageal PEC from baseline as well as difference between treatment groups will be presented by treatment group.

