Study Design: 
This Phase 2, randomized, double-blind, multi-center study will evaluate the efficacy, safety, and pharmacokinetics (PK) of etrasimod compared with placebo in adults with active EoE. The study will consist of a Screening Period of up to 35 days, 24 weeks of double-blind treatment (Double-Blind Treatment Period), 28 weeks of active extended treatment (Extension Treatment Period), and 4 weeks of follow-up (Safety Follow-Up Period) for a total study duration of up to 61 weeks.
 
Eligible subjects will be randomized in a double-blind fashion (3:3:2 ratio) to etrasimod 1 mg, etrasimod 2 mg, or matching placebo once daily. Randomization will be stratified by baseline history of esophageal dilation (yes/no) and concurrent proton pump inhibitor (PPI) therapy (yes/no).
 
All subjects who complete the Double-Blind Treatment Period and meet eligibility criteria for the Extension Treatment Period may enter the Extension Treatment Period. Subjects who were in the etrasimod 1 mg or etrasimod 2 mg groups in the Double-Blind Treatment Period will continue the same etrasimod dose in the Extension Treatment Period. Subjects who were in the placebo group during the Double-Blind Treatment Period will be re-randomized (1:1 ratio) to etrasimod 1 mg or etrasimod 2 mg at entry into the Extension Treatment Period.
 
Subjects will have follow-up visits at 2 and 4 weeks after the last dose of study treatment after Week 52 or the Early Termination (ET) Visit.

Number of Subjects (planned):

Approximately 96 subjects are planned to be enrolled.

Eligibility Criteria for the Double-Blind Treatment Period:

Key Inclusion Criteria (Full Inclusion Criteria Are Provided in the Protocol)

- Men or women between 18 and 65 years of age at the time of informed consent (IC)
- Have an EoE diagnosis prior to screening and histologically active disease with an esophageal peak eosinophil count (PEC) of ≥ 15 eosinophils (eos)/high power field (hpf) (~ 60 eos/mm²) from any level (proximal, mid, or distal) of the esophagus at the Screening esophagogastroduodenoscopy (EGD)
- Have dysphagia, defined as solid food going down slowly or getting stuck in the throat with an average frequency of ≥ 2 episodes per week over 2 weeks (as documented using the Dysphagia Symptom Questionnaire (DSQ) during the Screening period)

Key Exclusion Criteria (Full Exclusion Criteria Are Provided in the Protocol)

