Esophageal peak eosinophil count (PEC), EoE Histology Scoring System (HSS), DSQ, Food Avoidance Question (FAQ); Eosinophilic Esophagitis Endoscopic Reference Score (EREFS), Adult Eosinophilic Esophagitis Quality of Life (EoE-QOL-A), the Patient Global Impression of Change (PGIC), and Patient Global Impression of Severity (PGIS).

Primary efficacy endpoint:

- Percent change from Baseline in esophageal PEC at Week 16

Secondary efficacy endpoints:

- Absolute change from Baseline in DSQ score at Week 16
- Absolute change from Baseline in esophageal PEC at Week 16
- Proportion of subjects with esophageal PEC < 15 eos/hpf at Week 16
- Proportion of subjects with esophageal PEC \leq 6 eos/hpf at Week 16

A complete list of efficacy endpoints and definitions, as well as analysis methods will be provided in the Statistical Analysis Plan (SAP).

Pharmacokinetic Assessments:

Etrasimod plasma concentrations will be determined on Day 1 (predose and 4 hours \pm 15 minutes postdose) and before dosing at subsequent study visits and at the follow-up visits.

Collected blood for PK may also be used for profiling of drug binding proteins, bioanalytical method validation purposes, stability assessments, metabolite assessments, or to assess other actions of etrasimod with plasma constituents. Not all collected PK samples from placebo-treated subjects during the Double-Blind Treatment Period will be assayed.

Safety Assessments:

Safety will be assessed through the incidence of adverse events (AEs), clinical laboratory findings, 12-lead electrocardiograms (ECGs) (for first-dose monitoring, on treatment re-initiation after a defined period of treatment interruption, and at the start of the Extension Treatment Period, to be done predose and at 4 hours following the first dose), physical examinations, vital signs (measured hourly for at least 4 hours following the first dose), pulmonary function tests (PFTs), ophthalmoscopy and optical coherence tomography (OCT).

Statistical Methods:

CCI

Testing Strategy:

Unadjusted p-values for any hypothesis tests related to the comparisons of etrasimod dose group versus placebo will be reported. Estimated difference between etrasimod dose group and placebo as well as the associated 95% confidence intervals will be reported.

Statistical Analysis:

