measure that has been successfully used in clinical studies investigating the efficacy and safety of novel treatments for EoE.

The primary efficacy endpoint is the percent change from baseline in esophageal PEC at Week 16. The treatment effects of 2 etrasimod doses on the reduction of esophageal tissue eosinophils will be characterized. The secondary endpoints include measures of histologic, endoscopic, and symptomatic improvement for further elucidation of the effects of etrasimod on EoE disease activities.

These primary and secondary endpoints will be assessed at Week 16, and treatment will be continued in the Double-Blind Treatment Period until Week 24. The Week 16 timepoint was selected for primary and secondary efficacy assessments based on meaningful clinical and endoscopic improvements observed in UC patients following treatment with etrasimod. Data from Phase 2 studies APD334-003 and APD334-005 in adult subjects with moderately to severely active UC demonstrated that treatment with etrasimod 2 mg once daily for up to 46 weeks (n = 31) resulted in maximal improvements in the 2 cardinal symptoms of active UC, rectal bleeding and stool frequency, by Week 16, which were sustained through Week 46 [38,39]. Although there are notable differences between EoE and UC, both are IMIDs of the gastrointestinal (GI) tract. Based on etrasimod's mechanism of action and extrapolation on the time from etrasimod treatment initiation to observed clinical effects in patients with active UC, it is hypothesized that 16 weeks of etrasimod treatment will provide sufficient time to elicit the clinical effects of etrasimod in the treatment of patients with active EoE. Study treatment will be administered over 24 weeks in a double-blinded fashion and evaluation of histologic and patient-reported outcomes will occur at Weeks 16 and 24. Ultimately, a comparison of treatment effects observed at Week 16 compared to Week 24 will be performed to confirm that Week 16 is the timepoint at which the maximal treatment effects of etrasimod are observed in subjects with active EoE.

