2.4. ESTIMANDS

The primary and secondary estimands to support regulatory decisions are described in Table 1 below. Supplementary analyses for the primary and secondary estimands will be performed in the Modified Full Analysis Set (mFAS), Completers, and Per Protocol Set, respectively.

List of Estimands

Estimand	Definition	Attributes			
		Population	Variable/ Endpoint	Intercurrent event handling strategy	Population-level summary measure
Primary Estimand	Efficacy of etrasimod on esophageal peak eosinophil count (PEC) at Week 16	Full Analysis Set	Percentage change from Baseline in esophageal PEC at Week 16	Subjects with missing data for any reason (including early discontinuation) or who initiated rescue medication and/or rescue procedure before the primary efficacy assessments prior to Week 16 will have subsequent PEC data set to missing from that point forward through Week 24. The missing data at Week 16 will be imputed using a multiple imputation (MI) method.	Differences between etrasimod (2 mg, 1 mg and any dose) and placebo in percent change from Baseline in esophageal PEC at Week 16

Key Secondary Estimand 1	Efficacy of etrasimod on Dysphagia Symptom Questionnaire (DSQ) at Week 16	Full Analysis Set	Change from Baseline in DSQ at Week 16	Same as the intercurrent event handling strategy for the primary estimand	Differences between etrasimod (2 mg, 1 mg and any dose) and placebo in change from Baseline in DSQ at Week 16
Key Secondary Estimand 2	Efficacy of etrasimod on esophageal PEC at Week 16	Full Analysis Set	Change from Baseline in esophageal PEC at Week 16	Same as the intercurrent event handling strategy for the primary estimand	Difference between etrasimod (2 mg, 1 mg and any dose) and placebo in change from Baseline in esophageal PEC at Week 16
Key Secondary Estimand 3	Efficacy of etrasimod on esophageal PEC at Week 16	Full Analysis Set	Proportion of subjects with esophageal PEC < 15 eos/hpf at Week 16	Subjects in any of the following cases will be treated as nonresponders: use of rescue medication and/or rescue procedure prior to Week 16; premature discontinuation for study due to any reason prior to Week 16; or with missing data at Week 16 for any reason. If subject had rescue medication and/or rescue procedure after Week 16, any assessment after the rescue medication and/or rescue procedure time will be set to missing.	Difference between etrasimod (2 mg, 1 mg and any dose) and placebo in the proportion of responders at Week 16

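### For the primary endpoint the SAP plans a confidence interval only for the rank-score difference, not for the difference in percent change that its estimand names, and a table footnote contradicts the ranking

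*SAP*

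**What the plan says.** - **Estimand (SAP 2.4, List of Estimands).** The population-level summary for the primary estimand is "Differences between etrasimod (2 mg, 1 mg and any dose) and placebo in percent change from Baseline in esophageal PEC at Week 16". It does not say whether means or medians are compared.
- **Primary analysis (SAP 17.1.4).** An ANCOVA on rank scores is used because skewness and outliers are expected. Its output is LS mean rank scores and the "LS mean rank scores difference from placebo, 95% confidence interval (CI) and p-value". SAP 17.1.3 pools these rank results over 40 imputed datasets.
- **Percent-change scale (SAP 17.1.4; Protocol 11.5 is similar).** A "descriptive summary of percentage change in esophageal PEC from baseline as well as difference between treatment groups will be presented by treatment group". No interval is attached, and neither the statistic nor the handling of imputed values is given.
- **Planned Analyses by Endpoint table (SAP 17.2.1).** The ANCOVA column is ticked for percent change in PEC. Footnote a on that column says that the data are not ranked.
- **Week 24 (SAP 17.2.1, text after the table).** Percent change in PEC is analysed again with the same ANCOVA model.
- **Other Week 16 endpoints.** Absolute change in PEC has an unranked ANCOVA with LS mean differences and 95% CIs (SAP 17.2.3.1). The PEC responder endpoints have differences in proportions with 95% CIs (Protocol 11.5).

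**The concern.** The estimand and the estimator are on different scales. A difference in mean ranks shows how far two arms are separated relative to their spread in this sample. It does not say by how many percentage points PEC falls more on etrasimod than on placebo, which is what the estimand asks.

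The one planned figure on the percent-change scale has no stated precision. If it is a mean difference, it is also the summary that the SAP's reason for ranking treats as unreliable.

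The primary objectives in Protocol Section 2 include dose-response and dose selection. For those, the primary endpoint should give an effect size with an interval for each dose, not only a test. The footnote adds a second problem: read literally, the SAP prescribes both a ranked and an unranked primary model.

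**Working it through.** There is no effect size or SD for this endpoint in the visible text to reproduce; the sample-size section is redacted, which is not a defect. The check is whether a rank difference determines a percent-change difference.

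**Inputs from the documents**
- Size: "Approximately 96 subjects are planned to be enrolled" (Protocol Synopsis), allocated 3:3:2. Arms: 96 × 3/8 = 36 (1 mg), 36 (2 mg), 96 × 2/8 = 24 (placebo).
- Percent change = 100 × (R − 1), where R is Week 16 PEC divided by baseline PEC (SAP 6.6).

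**Assumptions, not from the documents**
- log R is normal with the same SD s in every arm, and the placebo median of R is 1.
- The 2 mg arm is shifted down by 0.8 s and the 1 mg arm by 0.4 s, with s = 0.4, 0.8 or 1.2.
- No covariates, no missing data.

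A log-normal model is used because percent change in a count cannot fall below −100%. A normal model with mean −70 and SD 60, for example, would put Φ(−0.5) = 31% of subjects below that limit.

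**Step 1: rank difference, 2 mg minus placebo, all three arms ranked together**
- P(2 mg value > placebo value) = Φ(−0.8/√2) = 0.286.
- P(2 mg > 1 mg) = P(1 mg > placebo) = Φ(−0.4/√2) = 0.389.
- Mean rank, 2 mg: 1 + 35 × 0.5 + 36 × 0.389 + 24 × 0.286 = 39.4.
- Mean rank, placebo: 1 + 23 × 0.5 + 36 × 0.611 + 36 × 0.714 = 60.2.
- Difference: 39.4 − 60.2 = −20.8, whatever the value of s.

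**Step 2: the same data on the percent-change scale**
- Difference in medians = 100 × (exp(−0.8 s) − 1).
- Difference in means = 100 × exp(s²/2) × (exp(−0.8 s) − 1).

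Simulated values (4,000 trials per setting) are in brackets. The last column is 1.96 times the simulated SD of the median difference (11.6, 22.5 and 32.9).

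| s | Simulated rank difference | Median difference, points | Mean difference, points | Approximate 95% half-width, median difference |
|---|---|---|---|---|
| 0.4 | −20.8 | −27.4 (−27.5) | −29.7 (−29.6) | 22.7 |
| 0.8 | −20.8 | −47.3 (−48.6) | −65.1 (−65.1) | 44.1 |
| 1.2 | −20.7 | −61.7 (−64.3) | −126.8 (−125.7) | 64.5 |

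One rank result fits median differences that vary more than twofold (61.7/27.4 = 2.3) and mean differences that vary more than fourfold (126.8/29.7 = 4.3). At s = 1.2 the mean difference is about twice the median difference (126.8/61.7 = 2.1), so it matters which of the two the descriptive summary reports.

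**Step 3: the two statements on ranking**
- SAP 17.1.4 ranks percent change in PEC. Protocol 11.5 does too, and drops ranking only for the key secondary continuous variables.
- Footnote a drops ranking for the whole ANCOVA column, and percent change in PEC is ticked in that column.
- Both cannot hold. The footnote fits the absolute-change row, so it was probably meant for that row only; this is an inference.

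**The case against.** **Other effect sizes exist.** A reader might infer that the trial yields no interpretable effect with uncertainty. The documents do not support that. Absolute PEC change and both responder endpoints come from the same biopsy at the same visit and carry 95% CIs, so they can inform dose selection and planning. This stands and limits the point to the primary estimand. It does not close the gap, because those are different estimands.

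**The protocol's general promise.** The Synopsis states: "Estimated difference between etrasimod dose group and placebo as well as the associated 95% confidence intervals will be reported". A reader might take this as a broken promise of a CI for the percent-change difference. The sentence names neither endpoint nor scale, and an interval for the rank difference meets it literally. The mismatch rests on SAP 2.4 against SAP 17.1.4.

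**Week 16 against Week 24.** Protocol 3.2 says that "a comparison of treatment effects observed at Week 16 compared to Week 24 will be performed". One might infer that rank differences at the two visits cannot be compared and that this aim fails. But the sentence is not tied to ranks, Protocol 11.5 plans descriptive percent-change differences for both weeks, and imputation gives both rankings the same subjects. Some endpoint lists are also redacted, so missing Week 24 analyses cannot be assumed.

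**Other routes to an interval.** Protocol 11.4.2 lists a mixed model on observed data as a sensitivity analysis. It ignores rescue use, so it answers another question, and the SAP table does not tick a mixed model for this endpoint. The arm-level n, mean and SD allow a rough unadjusted interval for a mean difference. That is true, but it is not prespecified, and it uses the summary that skewness makes doubtful.

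**Phase 2.** Tests are unadjusted, and exposure-response modelling is planned separately. This lowers the severity but does not align estimand and estimator.

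**Conclusion.** The concern holds in limited form. For the primary endpoint, the only confidence interval that SAP 17.1.4 specifies is on the rank scale. The quantity named in the estimand is descriptive, with statistic, data basis and precision all left open. Footnote a contradicts the ranked model and must be reconciled with it.

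On size, a rank difference of about −21 is compatible with median differences from about −27 to −62 points and mean differences from about −30 to −127. These ranges depend on the assumed log-normal model, the 0.8 SD shift and log-SDs of 0.4 to 1.2. They illustrate the missing link between scales and do not predict the trial's result.

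The validity of the rank test is not in question, and the trial as a whole does produce interpretable Week 16 effects with intervals. This is an inexpensive improvement that lets the trial estimate its own primary estimand.

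**What to change.** 1. Keep the rank ANCOVA as the source of the primary p-value.
2. In each of the 40 imputed datasets, fit a median regression of percent change in PEC on treatment, the two stratification factors and baseline PEC, with a bootstrap standard error. Pool by Rubin's rules and report the adjusted median difference for each dose against placebo with a 95% CI, at Weeks 16 and 24. The estimand also names any dose, so the same can be done for that comparison (72 against 24).
3. In SAP 2.4, state the summary measure as a difference in medians, adjusted for the strata and baseline PEC.
4. State that the p-value comes from the rank test and the effect size from the median regression, since the two can disagree near the 0.05 level.
5. For the descriptive summary, say whether the difference is a mean or a median, and whether data are observed or imputed.
6. Correct footnote a so that it does not apply to percent change in PEC.

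Cost: a few lines of SAP text, including the revised estimand entry, and one extra procedure per imputed dataset. Sample size, data collection and the test do not change. With about 36 against 24 subjects per comparison the interval will be fairly wide: roughly ±23 to ±65 points under the assumptions above, before covariate adjustment and imputation.

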17.1.5. SUPPLEMENTARY ANALYSIS OF PRIMARY EFFICACY VARIABLE(S)

The primary model as described in Section 16.1.3 will be repeated using the Completers Set and Per Protocol Set as

supplementary analyses. Subgroup analyses will also be performed for the primary model.

17.1.6. SENSITIVITY ANALYSIS OF PRIMARY EFFICACY VARIABLE(S)

Sensitivity analyses will be implemented to explore different types of missing data approaches.

17.1.6.1. Tipping Point Analysis

A tipping point approach based on multiple imputation of values through Week 16 will be used with a specified adjustment (referred to as delta adjustment or shift) applied to values imputed under a MNAR-based imputation model. To find a tipping point, a series of imputations will be performed with increasing values of delta.

The goal is to evaluate the plausibility of the assumed expected values for missing outcomes on each treatment group under which the conclusions change, ie, under which values of delta there are no longer evidence of significant treatment difference.

The following steps will be implemented:

Step 1:

Same as Step 1 described in 16.1.2 above.

Step 2:

Apply a shift (i.e. additive delta adjustment) to the imputed PEC at each visit in both treatment groups. Percent change from Baseline in PEC will be re-computed at Week 16 for each of the 40 imputed datasets.

Step 3:

Same as Step 3 described in 16.1.2 above.

Step 4:

Same as Step 4 described in 16.1.2 above.

Note, imputations with delta adjustment will be performed with progressively increasing delta values until a tipping point is reached based on the significance of the ANCOVA test based on rank scores. A tipping point will correspond to the smallest value of delta for which the primary hypothesis is no longer rejected. The shift parameter (delta) for the active treatment group will take increasing values from 0 with increments of 40 (maximum PEC of X), representing adjustments in towards worse outcomes (i.e., after dropout, on average, subjects on treatment will have PEC worsen). For placebo arm, delta adjustments will decrease with increments of 40, representing adjustments in the direction of better outcomes. The adjustments in each treatment group will be continued until the ANCOVA test based on rank scores for the primary hypotheses are no longer significant at the 2sided α level, 0.05. The corresponding shift parameters in both treatment groups at the tipping point will be reported along with the LS means rank scores, LS mean rank scores difference from placebo, 95% CI, and p-values from each ANCOVA test based on rank scores.

Results will be plotted as a heat map on a two-dimensional plot with axes corresponding to the delta values used in each treatment group respectively, and different colors will be used to represent the magnitude of the 2-sided p-values corresponding to analysis with each combination of delta values. The clinical interpretation about the plausibility of the assumptions underlying the tipping point will be provided in the CSR.

